10.3.2 No Data on Methadone Maintenance OTP for Most Sites

It is possible that availability of PC treatment of OUDs could shift patients from OTPs into PC, in contrast to initiating new patients into OUD treatment. Also, the MA Model is expected to increase treatment in OTPs because some patients seeking buprenorphine will not be appropriate candidates for PC management or they will need to transfer to more structured programs. Ideally, we would therefore have OTP data from all sites. However, that was not possible: we could only obtain claims for methadone OTPs for all patients at one site (KPW) and 30% of patients at another (HF). Another site (MF) had one internal OTP program. However, even when OTP claims were available, estimating our outcome “days of OUD treatment” from the claims required a large

number of assumptions. Therefore, a decision was made to use only evidence-based medication treatments provided in medical settings (buprenorphine and injectable extended-release naltrexone) in calculating days of OUD treatment. Nevertheless, to address the limitation of not having a measure of days treated with methadone from OTPs for all sites, we will conduct analyses using the available methadone maintenance data from 3 sites to evaluate whether implementation of the MA Model impacts utilization of methadone (in addition to buprenorphine and injectable naltrexone), and whether including OTP data changes our main results.

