## 4.0 OUTCOME MEASURES

### 4.1 Definition of Primary Implementation Outcome Measure

The primary outcome (clinic-level measure) is the number of patient days of OUD medication treatment documented in the EHR in each clinic post-randomization. To account for varying clinic sizes, the clinic-level outcome is divided by the number of patients seen in the clinic post-randomization and then multiplied by an appropriate scaling factor in order to report the results (e.g., multiplying by 10,000 to calculate the number of patient days of OUD treatment per 10,000 patients), and reported as patient-years of treatment provided by a clinic (calculated by simply dividing days of OUD treatment by 365).

“OUD medication treatment” includes medications for OUD that can be prescribed in PC and documented in EHRs—buprenorphine formulations indicated for OUD (oral, implants, sustained release injection with or without an OUD diagnosis) or injectable extended release (XR) naltrexone with a diagnosis of OUD. An OUD diagnosis is required for injectable XR naltrexone because it is often used for alcohol use disorders (AUD). We do not require an OUD diagnosis for buprenorphine because there are buprenorphine formulations specific for OUD and PROUD Phase 1 analyses revealed OUD diagnoses are often missing, consistent with the literature. Further, an OUD diagnosis is likely to be documented by PROUD clinic providers based on the PROUD NCM manual, so that requiring an OUD diagnosis could bias findings toward favoring the intervention clinics.

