#### **5.2.4.d. Incorporating Limited Data on Methadone Maintenance Therapy (MMT)**

We will describe the availability of MMT by health system. For health systems with methadone maintenance outpatient treatment programs (OTPs) data available (one HCS and possibly a second), we will incorporate procedure codes for Methadone Maintenance OTPs when estimating the objective 1 main implementation outcome in this analysis. Based on consultation with addiction medicine specialists, we will require at least 2 procedure codes to be included as using Methadone Maintenance from an OTP and assume that treatment lasts for the time period between codes for a maximum of 365 days per code (e.g., 2 codes 365 days apart). The end date of MMT (i.e., last claim) will be estimated at half the average days between previous MMT codes.

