#### **7.6 Descriptive Information on Data Sources**

We will describe the proportion of patients within each HCS with claims data available, which is expected to include most of the sample for one of the HCS and 10-30% enrolled patients from a second HCS. We will look at this overall and by clinic (intervention vs. control).

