f Prescribers determined from medication orders in the electronic health records. Providers assigned to clinics based on number of visits with patients in the clinic post-randomization.

Abbreviations: NCM – nurse care manager; ITT- intent to treat; OUD: opioid use disorder; SD – standard deviation; XR-NTX – extended release injectable naltrexone

Supplemental Table 1a is the main Table 1a above by health system
Supplemental Table 1b is the main Table 1b above by health system
Supplemental Table 2 is the main Table 1a above but using data for the post randomization period and among patients with an eligible visit post randomization (closest to study end as anchor for variables)
Supplemental Table 3 is the main Table 2 above by health system

Supplemental Table 4 is the main Table 2 above with OUD treatment related outcomes stratified by newly initiated treatmenta versus on-going treatmentb, and the OUD diagnosis outcome stratified by newly diagnosed OUDc versus prevalent OUDd.
 
a OUD treatment in the 2 years post randomization and no OUD treatment in the prior 365 days
 
b OUD treatment post-randomization that does not meet criteria for initiated above
 
c 1+ OUD diagnosis anywhere in the health system in the 2 years post randomization and no OUD diagnosis in the 2 years pre randomization.
 
d 1+ OUD diagnoses in both the 2 years pre randomization and 2-years post randomization

Supplementary Table 5. Sensitivity analyses focused on assumptions made in estimating patient-years of OUD medication treatment, clinic-level results in the 2 years post randomization			
	Patient years treatment /10,000 patients seen in clinic post-randomizationa		Mean difference (95% CI)b
	6 intervention clinics	6 usual care clinics	
Primary outcome			---
Limited to the time period in which the NCM started seeing patients d			
Limited to health systems that successfully implement the MA model e			
Covariate adjusted c			
Using a combination of medication orders and pharmacy dispensings			
Adding Methadone Maintenance Therapy data from 1-2 sites, per 10,000 patients seen in the 1-2 clinics post randomization			
Adding pharmacy dispensings and MMT data at the 1-2 sites with these sources of data			

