For each dispensing, if its rxdate is in “the range” of an order date or a refill date, then it is considered to be linked to that order or refill and dropped in calculations; otherwise, this dispensing is considered as not linked to any order and added to the calculation of days covered. The range is defined as dispensed within 30 days after the order/refill’s start date (an order’s start date is the order’s date; a refill’s start date is derived from the original order’s date and days supply).

This calculation will be done after all data cleaning and imputation.

- 1) A SA that adds in procedure codes for methadone maintenance therapy at sites where this data is available
- 2) A SA that combines SA # 3 and #4 at sites with both dispensing and methadone maintenance therapy data.

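### If the insurer system with 10–30% claims coverage is included, the methadone sensitivity analysis would still show 70–90% of a methadone-to-buprenorphine switch there as a net gain

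*SAP*

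**What the plan says.** **Purpose.** Protocol 10.3.2 gives the reason for looking at methadone: "It is possible that availability of PC treatment of OUDs could shift patients from OTPs into PC". It promises to examine whether adding opioid treatment program (OTP) data alters the main result.

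**Analysis.** SAP 5.2.4.d describes its scope as "For health systems with methadone maintenance outpatient treatment programs (OTPs) data available (one HCS and possibly a second". Section 5.2.4.e repeats the exercise with dispensing data added. Appendix A has the matching line, "A SA that adds in procedure codes for methadone maintenance therapy at sites where this data is available". The Supplementary Table 5 row reads "Adding Methadone Maintenance Therapy data from 1-2 sites, per 10,000 patients seen in the 1-2 clinics post randomization". This keeps the scaling of the primary outcome, in which "the clinic-level outcome is divided by the number of patients seen in the clinic post-randomization" (SAP 4.1).

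**Data capture.** SAP 4.1.1 takes buprenorphine from medication orders, available at all six systems. It takes procedure codes from the EHR everywhere and from claims at two systems. SAP 8.1 treats any care with no record as not having happened. On claims, SAP 7.6 expects coverage "which is expected to include most of the sample for one of the HCS and 10-30% enrolled patients from a second HCS". Protocol 10.3.2 says "we could only obtain claims for methadone OTPs for all patients at one site (KPW) and 30% of patients at another (HF". Protocol 8.1 adds a third source: utilization data from an internal OTP at Montefiore.

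**Enrolled samples.** Protocol 6.0 (item 4), 6.5 and 11.8 plan enrolled samples at the two health plans to check the visit-based sample and its measures. The SAP specifies an enrolled-sample analysis for Objective 2 only (5.4.3 and 8.1).

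**The concern.** The two parts of the numerator cover different people. Buprenorphine and extended-release naltrexone are counted for everyone assigned to the clinic. At an insurer system, methadone is counted mainly for people whose claims reach the plan, and for the rest it is entered as zero. A patient without claims who moves from an OTP to primary-care buprenorphine therefore goes from zero recorded days to fully recorded days, although total treatment has not changed.

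The analysis exists to separate new treatment from relocated treatment. Where coverage is low, it would report that the intervention's gain survives the addition of methadone mainly because it could not see the methadone. The danger is that this row is later cited as evidence against substitution.

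**Working it through.** The documents give no power or bias figure for this analysis, so there is nothing to reproduce. The check is direct arithmetic.

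**Inputs**
- M: treatment days moved from methadone to buprenorphine, with total treatment unchanged.
- Capture of buprenorphine: 1 (orders, SAP 4.1.1).
- Capture of methadone: c, taken as the claims-covered share. For the partly insured system, c = 0.10 to 0.30 (SAP 7.6), or 0.30 (protocol 10.3.2). For the other, c = 1.0 from the protocol. The SAP says only that most of the sample is covered, so I assume 0.8 to 1.0.
- N: all patients seen (SAP 4.1; Supplementary Table 5).

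**Step 1. One system.** Recorded change = M − cM = (1 − c)M. The true change is 0.
- c = 0.10: 0.90M
- c = 0.30: 0.70M
- c = 0.80: 0.20M
- c = 1.00: 0

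**Step 2. Does baseline adjustment help?** Suppose both clinics have M methadone days before randomization. Both then have a recorded baseline of cM, so the covariate is equal and removes nothing. After randomization the switching clinic records M and the other still records cM. The difference is again (1 − c)M.

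**Step 3. Both insurer systems together.** Weight clinics equally, since the clinic is the unit of analysis, and assume the same M per 10,000 at each system. The residual share is [(1 − c1) + (1 − c2)]/2.
- c1 = 1.0: (0 + 0.70)/2 = 35% to (0 + 0.90)/2 = 45%
- c1 = 0.8: (0.20 + 0.70)/2 = 45% to (0.20 + 0.90)/2 = 55%

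**Step 4. Which repair works?**
- Restrict only the denominator to claims-covered patients: (M − cM)/(cN) = [(1 − c)/c] × M/N. This is 0.70/0.30 = 2.33 times M/N at c = 0.30, and 0.90/0.10 = 9 times M/N at c = 0.10. Both are worse than no change.
- Restrict numerator and denominator: (cM − cM)/(cN) = 0 at every c, provided the code rule finds the methadone days of enrolled patients.

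The false gain therefore arises in the numerator. The all-patient denominator only rescales it.

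**The case against.** The strongest reply is that the problem is conditional. The SAP commits to one system and only possibly a second, and names neither. The system with claims on all or most patients is the natural definite one, and there a switch cancels or nearly so. The second could be the system with the internal OTP, whose data are not claims. This stands. A reader might infer that the whole analysis sees methadone only through claims and is blind to substitution everywhere, and the documents do not support that. What remains is that nothing in the SAP excludes the partly insured system. If the internal-OTP system is used instead, methadone from outside programs is still not captured.

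A second reply is that the limitation is disclosed. Section 5.2.4.d is headed as using limited data and will describe methadone availability by system. Section 7.6 reports claims coverage by system and clinic, and 7.7 reports outcomes by arm within system. This will help a careful reader, but none of it changes the calculation.

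A third is that little rests on one sensitivity row covering two to four clinics. This is true, and it limits the weight of the point.

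Two stronger readings are tempting and should be left aside:
- **Unequal coverage between the two clinics creating a false arm difference.** The 10–30% is an expected range for one system. No section reports different coverage by clinic, and a stable difference would also appear in the baseline covariate.
- **The methadone day count as a further distortion in the same direction.** The SAP will "assume that treatment lasts for the time period between codes for a maximum of 365 days per code", on the advice of addiction medicine specialists. If that overcounts methadone, the days lost on switching look larger and the apparent gain shrinks. The 60-day gap in SAP Table 2 defines a separate discontinuation outcome, and nothing requires its use here.

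**Conclusion.** The point holds in conditional form. At an insurer system with 10–30% claims coverage, 70–90% of a pure methadone-to-buprenorphine switch would remain as an apparent gain. With both insurer systems in the row, the share is roughly 35–55%. At the near-complete system alone it is 0–20%, and 0 if the protocol's statement of full coverage is right.

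These figures assume that c equals the claims-covered share. EHR procedure codes for patients without claims would raise it, and different methadone use among enrollees would move it either way.

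A reader might want the size in patient-years, but the documents do not support one. The non-zero methadone prevalences in protocol Table 2 are 0.10% at Kaiser Permanente Washington and 0.01% at Multicare. Applying 0.10% to Henry Ford, where the protocol puts the 30% coverage, would exceed that system's entire recorded OUD prevalence of 0.09%.

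The primary test is untouched. What fails is the ability of this row to rule out substitution at a partly covered system.

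**What to change.** In SAP 5.2.4.d, 5.2.4.e, Appendix A and the Supplementary Table 5 shell, choose one of the following and state it:
1. At insurer systems, compute this outcome only in health-plan-enrolled patients and enrolled time. Apply the restriction to every numerator component (buprenorphine, extended-release naltrexone, methadone), to the denominator and to the baseline value. Restricting the denominator alone would enlarge the error.
2. Limit the row to the system with near-complete methadone data.

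Name the systems used. If the internal-OTP system is one of them, add that methadone from external programs is not captured there.

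The cost is SAP wording and some programming. Enrollment dates are already collected for both health plans (protocol Table 4) and used in SAP 5.4.3, although the baseline value needs pre-randomization enrollment as well. The downside is a smaller sample at the partly insured system under option 1, or the loss of that system from the row under option 2. The methadone day-count rule need not change for this purpose.

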### **A3. Combine OUD Treatments of Buprenorphine and Naltrexone**

- 1) Order all OUD treatments by their respective start and runout dates. See Examples below.
- 2) During time periods of interest, consider it a day “covered” by OUD treatment during the period of interest if there is buprenorphine or injectable naltrexone that covers that day based on start and runout dates. Do not double count covered days.
- 3) Estimate start and end dates for each continuous episode (continuous defined as a gap  $\leq 7$  days between runout date of one OUD treatment and start date of the next

treatment OR  $\leq 14$  days between end date of one buprenorphine prescription and start date of naltrexone) based on days covered for all the buprenorphine and naltrexone in the time period of interest.

- 4) Any gaps not meeting these criteria above result in the end of a continuous episode and these gaps between episodes are NOT part of any episode and do not contribute to treatment days. See examples below.
- 5) Pre and post randomization episodes are not allowed to overlap. They will be left and right censored accordingly. For example, a treatment episode of 90 days with 15 days in the post randomization period (includes randomization date) will be split into two episodes with one episode contributing 75 days of treatment pre-randomization and a second episode contributing 15 days of treatment post randomization.
- 6) OUD treatment days = sum of all episodes [(episode end date – episode start date) + 1] in the pre and post randomization periods.

Examples 1-8 below are each a single patient's prescriptions. These examples are shortened to a 20-day period of interest as an example only. Our perspective here is the prescribers' "intent to treat" (i.e., we do not know how or if patients actually took the oral medications but the assumptions we are making are typical of studies that use electronic health data for studying medication treatment and adherence). (Bup=buprenorphine; NTX=naltrexone)

Example 1: Bup	TIME PERIOD OF INTEREST																				
	-1	1	2	3	4	5	6	7	8	9	10	11	12	13	14	15	16	17	18	19	20
Bup1																					
Bup2																					
Bup3																					
Bup4																					
Bup5																					

Bup 1 covers day 1 (from a rx occurring during -90 days of period of interest as depicted by coverage on -1 day) and ends day 8; Bup 2 starts day 8 and ends day 11; Bup 3 starts day 12 and ends day 15; Bup 4 starts day 15 and ends day 16; Bup 5 starts day 19 and covers day 19 and 20 – may end on day 20 or after period of interest (truncated).

One continuous episode: Day 1 to Day 20. The gap (day 17 and day 18) is 2 days ( $\leq 7$  days) so smooth it to be continuous.

20 of the 20 day time period of interest is covered by treatment.

Example 2: Bup	TIME PERIOD OF INTEREST																			
	1	2	3	4	5	6	7	8	9	10	11	12	13	14	15	16	17	18	19	20
Bup1																				
Bup2																				
Bup3																				
Bup4																				
Bup5																				

Bup 1 covers day 1 and ends day 6; Bup 2 starts day 1 and ends day 11; Bup 3 starts day 6 and ends day 8; Bup 4 starts day 15 and ends day 16; Bup 5 starts day 16 and ends day 19.

One continuous episode: Day 1 to Day 20. The gap is 4 days ( $\leq 7$  days) so smooth it to be continuous.

Example 3: Bup & NTX	TIME PERIOD OF INTEREST																			
	1	2	3	4	5	6	7	8	9	10	11	12	13	14	15	16	17	18	19	20
Bup1																				
NTX1																				

Bup 1 covers day 1 and ends day 4; NTX1 starts day 10 and covers through day 20 (right truncated since end date would be past time period of interest of 20 days).
 
One continuous episode: Day 1 to Day 20. The gaps in treatment (day 5-9) are <math>\leq 14</math> days.
 
20 of the 20 day time period of interest are covered by treatment.
																				

Example 4: Bup & NTX	TIME PERIOD OF INTEREST																			
	1	2	3	4	5	6	7	8	9	10	11	12	13	14	15	16	17	18	19	20
NTX1																				
Bup1																				

NTX1 1 covers day 1 and ends day 9 (left truncated because it must have begun prior to day 1 given inj ntx lasts 28 days); Bup1 starts day 18 and covers though day 20 (likely right truncated) in the period of interest.
 
Two continuous episodes: 1st episode is Day 1 to Day 9. Then there is a gap <math>>7</math> days so a new episode begins. 2nd episode starts day 18 and ends day 20.
 
12 of the 20 day time period of interest are covered by treatment.
																				

Example 5: Bup	TIME PERIOD OF INTEREST																			
	1	2	3	4	5	6	7	8	9	10	11	12	13	14	15	16	17	18	19	20
Bup1																				
Bup2																				

BP1 1 covers day 1 and ends day 9 (possibly left truncated if it began prior to day 1; Bup2 starts day 7 and covers though day 17).
 
One continuous episode: Day 1 to Day 17. No double counting of overlap days (7-9).
 
17 of the 20 day time period of interest are covered by treatment.
																				

Example 6: Bup & NTX	TIME PERIOD OF INTEREST																			
	1	2	3	4	5	6	7	8	9	10	11	12	13	14	15	16	17	18	19	20
Bup1																				
NTX1																				
NTX2																				

BP1 1 covers day 1 and ends day 4 (possibly left truncated if it began prior to day 1; NTX1 also covers day 1 and ends day 4 (left truncated); NTX2 starts day 10 and ends day 20 (right truncated)
 
One continuous episode: Day 1 to Day 20. The gap is 5 days (<math>\leq 7</math>) so smooth it to be continuous.
																				

Example 7: Bup & NTX	TIME PERIOD OF INTEREST																			
	1	2	3	4	5	6	7	8	9	10	11	12	13	14	15	16	17	18	19	20
Bup1																				
NTX1																				
NTX2																				

BP1 1 covers day 1 and ends day 4 (possibly left truncated if it began prior to day 1; NTX1 covers day 1 and ends day 3 (left truncated); NTX2 starts day 10 and ends day 20 (right truncated).

One episode: Day 1 to Day 20. No double counting of overlap in days between bup1 and ntx1. There is  $\leq 14$  day gap between when bup1 ends (last drug before NTX2) and when NTX2 starts so it is continuous.

20 of the 20 day time period of interest are covered by treatment.

Example 8: Bup & NTX	TIME PERIOD OF INTEREST																			
	1	2	3	4	5	6	7	8	9	10	11	12	13	14	15	16	17	18	19	20
Bup1																				
NTX1																				
NTX2																				

BP1 1 covers day 1 and ends day 4 (possibly left truncated if it began prior to day 1; NTX1 covers day 1 and ends day 5 (left truncated); NTX2 starts day 10 and ends day 20 (right truncated).

One continuous episode: Day 1 to Day 20. The gap is 4 days ( $\leq 7$ ) so smooth it to be continuous.

## Appendix B. Initial Values for Power Simulations

The following is a justification of the initial values used in Step 2 of the data generation model for the Primary Objective 1 Outcome power simulations.

Consider a lag-1 autoregressive time series given by

$$y_{t+1} = \xi + \psi y_t + e$$

where  $\xi$  and  $\psi$  are constants,  $e$  is normally distributed with mean zero and variance  $\sigma_e^2$  and  $t$  indexes time interval. Letting  $\eta$  denote the mean of any particular  $y_t$ , and  $\varsigma$  the variance, then we have

$$\begin{aligned} E(y_{t+1}) &= \xi + \psi E(y_t) \\ \Rightarrow \eta &= \xi + \psi \eta \\ \Rightarrow \eta &= \frac{\xi}{1 - \psi} \end{aligned}$$

and

$$\begin{aligned} Var(y_{t+1}) &= \psi^2 Var(y_t) + Var(e) \\ \Rightarrow \varsigma &= \psi^2 \varsigma + \sigma_e^2 \\ \Rightarrow \varsigma &= \frac{\sigma_e^2}{1 - \psi^2}. \end{aligned}$$

## **Appendix C. Small-sample Degree of Freedom (DF) Correction Method for Objective 2 Primary Analysis**

Recent literature has highlighted the need to incorporate small-sample correction methods when analyzing data from cluster-randomized trials (CRTs) when there are few (e.g., <30) clusters (Kahan et al. 2016; Leyrat et al. 2017). In particular, it has been documented that when there are few clusters the usual approaches to analyzing correlated data in CRTs, including generalized estimating equations (GEE) and generalized linear mixed models (GLMM; the proposed analysis approach), can yield inflated type 1 error rates (Kahan et al. 2016). For example, applying a traditional test based on these models that has a nominal type 1 error rate of 5%, may lead to actual type 1 error rates that are much larger (e.g., 10-20%) such that we would reject the null hypothesis that the intervention is effective, even if it is truly not effective, above the pre-specified acceptable level.

Although corrections for tests of treatment effects under GLMM with few clusters have been studied, there remain gaps in knowledge of which test to use in the context of PROUD Objective 2 analyses. In particular, although it is common to adjust for covariates (such as the baseline value of the outcome as in PROUD analyses), covariate-adjusted analyses have not received attention in existing literature. Moreover, despite extensive research on corrections when the outcome is continuous or binary, to our knowledge the performance of the methods for count outcomes (such as the number of days of acute care utilization) has not been studied.

[figure not shown]
To address these gaps in the statistical literature (and to gain insight on how to account for the small number of clusters for PROUD Objective 2 analyses), we investigated the performance of various testing procedures for GLMM via simulation. The tests we considered were all eight combinations of two forms of test and four methods to compute the denominator degree of freedom (DDF). The forms of test we considered were the Wald t-test and the likelihood ratio F-test (LRT). The methods to compute DDF we considered were residual, containment, between-within 1 (BW1), and between-with 2 (BW2) (also referred to as “inner-outer”). BW1 and BW2 are two generalizations of the BW method to covariate-adjusted models, and BW has been shown to perform well via various scenarios in simulation (Li & Redden 2015).

We conducted simulations for count outcomes (i.e., Poisson GLMM) with various numbers of clusters, mean and coefficient of variation (CV) of clusters sizes, and intraclass correlation coefficients (ICC) characterizing the correlation of patients within a cluster. We also vary the number and the level (individual- vs. cluster-level) of (i) prognostic variables in the data-generating model, and (ii) extra (i.e., non-prognostic) covariates in the correctly specified fitted model. We consider including extra covariates to account for the potential that non-prognostic covariates may be included in secondary analyses. Additional details on the simulation study setup are described in a manuscript in preparation and are available upon request.

[figure not shown]
